Study protocol and statistical analysis plan

Evaluation of the Effectiveness of Extracorporeal Shockwave Therapy in Patients With Patellar Tendinopathy on Its Micromorphology

NCT number: NCT06102421

Date: October 4, 2023

(Date of approval of the project by the ethics committee)

Study design and description

This work is designed as a prospective cohort study, in which the effects of low-energy focused extracorporeal shock wave therapy (ESWT) in patients with patellar tendinopathy (PT) on its micromorphology will be monitored. It is estimated that at least 21 patients will participate. In addition, there will be a small control group of healthy tendons which will be monitored to observe magnitude of natural changes.

Patients in both groups will have same program. The research within one patient will last a total of 16 weeks from the initial to the final examination. Potential participants will be selected based on the recommendation of a specialist doctor and their suitability will be assessed according to the inclusion criteria. They will then be invited to an initial examination. This will include an objective examination by a physiotherapist, a subjective assessment by the patient and an ultrasonographic (USG) examination followed by a micromorphological analysis using special software.

Patient selection

Patient will be included in the study if they meet these inclusion criteria:

- is a recreational athlete performing intensive sport activity loading patellar tendon (running, jumping, strength training etc.) at least 3 days in a week for minimum of 1 hour per session,
- is in age between 18-40 years,
- has a patellar tendon pain, which limits (at least in part) the quality of normal daily or sports activities,
- has clinical manifestation of PT (pain and impaired function) confirmed by clinician,
- has symptoms only in one leg, the other one is asymptomatic.

Patient will not be included if:

- any contraindication for ESWT is present (according to International Society for Medical Shockwave Treatment (ISMST) consensus at https://shockwavetherapy.org),
- is aware of any symptomatic mechanical tendon damage in the past (e.g., partial or complete rupture in relation to the injury),
- neurological, oncological, or systemic disease (e.g., neuropathy, lupus or rheumatic arthritis) coexists,
- is/was already treated for PT elsewhere (e.g., platelet-rich plasma therapy, physiotherapy)
- is using blood thinning medications or statins.

Initial and final examination

During the initial and final examinations, the several tasks to the patient will be performed. Firstly the anamnestic data will be collected, then the area of greatest pain will be localized by palpation.

Secondly, the patient will be asked to complete a validated Victorian Institute of Sports Assessment - Patella questionnaire, which assesses the subjectively perceived severity of the disease and partly its impact on the quality of normal daily or sports activities.

The patient's maximal pain will be assessed using a standardized numerical rating scale (NRS) of pain. The patient will be asked about the morning and maximum pain that could be caused by various factors.

Lastly, the ultrasonographic (US) examination of patient's AT in both legs will be performed. This examination is described in the following chapter.

Both, initial and final examinations in each patient will be performed by only one person (the investigator of the study). Follow-ups will be in the day of the last ESWT application (for NRS and VISA-P) and at 15 week (for all outcomes)

Ultrasonographic examination

US examination will be performed with a Mindray DC-70 machine with a linear probe type L12-3E with a frequency of 12 Hz in the preset "MSK" mode. The whole area of patellar tendon will be monitored from the apex patellae to the insertion site on the tibia by longitudinal and transverse imaging.

The values of anteroposterior tendon width at the anteroposterior widest point will be collected using the measuring instruments included in USG machine.

After that, the preset will be changed to the specific setting, and three pictures of each leg (symptomatic and asymptomatic) will be saved in long axis for subsequent micromorphological analysis using Spatial Frequency Analysis software (SFA). SFA is a non-invasive, specialized method which analyzes the US image. In particular, it analyzes the anisotropic B-mode speckle pattern arising from within a tissue type in the spatial frequency domain and is capable of detecting and comparing collagen fascicles organization, spacing, and density across various parameters. Mean of those three values will be used for statistical analysis.

ESWT application

The low-energy focused ESWT will be applied using the BTL-6000 FSWT machine with piezoelectric generator and a coupling pad which modulates penetration depth to 0-35 mm. The setting is chosen based on ISMST guidelines (https://shockwavetherapy.org): Energy Flux Density (EFD) between 0.14-0.18 mJ/mm2 due to patient tolerance, frequency at 5 Hz. A total of 2000 shocks will be applied semi-statically to the most US defined pathological area in patellar tendon followed by 2000 shocks dynamically to the quadriceps muscle always using a contact gel. The set parameters will not change during the study and will remain the same for each patient.

Data analysis

The normality of the data distribution will be determined by calculating the Shapiro-Wilk p value. Independent t-tests (or Mann Whitney U tests for non-parametric) will be performed for each parameter to compare baseline values between symptomatic and asymptomatic limb for US and SFA parameters. In addition, paired t-tests (or Wilcoxon tests) will be performed for each parameter, evaluated in each group separately (symptomatic, asymptomatic) between baseline and final values. To reach effect size, Cohen's d will be calculated for paired t-tests and biserial rank correlation for non-parametric Wilcoxon test.

Intergroup statistical significance between baseline and follow-up values of morphological parameters will be evaluated using two-way ANOVA or non-parametric Kruskal-Wallis test. Statistical significance between time periods in VISA-P and NRS parameters will be evaluated using repeated measures ANOVA or non-parametric Friedman test with repeated measures.

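### Neither healthy tendons nor the asymptomatic leg can show how an untreated symptomatic tendon changes, so the planned tests cannot support a claim of ESWT effectiveness

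*Combined protocol and SAP*

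**What the plan says.** The document is titled "Evaluation of the Effectiveness of Extracorporeal Shockwave Therapy in Patients With Patellar Tendinopathy on Its Micromorphology". Under Study design and description it states: "This work is designed as a prospective cohort study", and "It is estimated that at least 21 patients will participate". On the control group it says that "there will be a small control group of healthy tendons which will be monitored to observe magnitude of natural changes". The size of that group is not given.

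Under Patient selection, a patient qualifies who "has a patellar tendon pain, which limits (at least in part) the quality of normal daily or sports activities" and who "has clinical manifestation of PT (pain and impaired function) confirmed by clinician". Symptoms must be confined to one leg, and earlier or current treatment for the condition elsewhere is an exclusion. Eligibility is assessed first and the initial examination follows. No untreated or sham-treated tendinopathy group, run-in or second pre-treatment measurement is described.

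Under Initial and final examination, history is taken at both examinations without its content being specified. VISA-P and NRS are repeated on the day of the last ESWT, and all outcomes at week 15. The design section gives 16 weeks from first to last examination.

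Under Data analysis, US and SFA parameters are tested before against after, "evaluated in each group separately (symptomatic, asymptomatic) between baseline and final values". A two-way ANOVA or Kruskal-Wallis test compares groups on the morphological parameters. VISA-P and NRS are tested over time only.

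**The concern.** The plan asks healthy tendons to show the size of natural change. They can show drift and measurement variation in normal tendon. They cannot show the untreated course of a painful, diseased one, because they have nothing to recover from. The same holds for the asymptomatic leg. For VISA-P and NRS there is no planned between-group comparison at all.

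If symptomatic tendons change after ESWT while the comparators stay flat, the natural reading is that ESWT worked. The same pattern appears with no ESWT effect whenever symptomatic tendons improve by themselves, or patients change their sport load or receive other treatment during follow-up. What is at stake is the word effectiveness in the title. The data would still describe change after ESWT.

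**Working it through.** **The plan's own figure.** The only sample-size figure is 21, with no alpha, power, effect size or SD, so it cannot be reproduced. For orientation, a paired t-test with n = 21 at an assumed two-sided 0.05 has 80% power at a standardised change of 0.64 and 90% at 0.74. The figure fits many inputs and confirms none.

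**What each planned test can separate.**

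- *Paired test in symptomatic tendons:* measures the total change, from ESWT and from everything else.
- *Paired test in asymptomatic tendons:* measures drift in tendons without symptoms.
- *Two-way ANOVA or Kruskal-Wallis:* even read as a difference in change, it removes only what the two kinds of tendon share. Recovery confined to symptomatic tendons stays in the contrast.
- *Repeated measures ANOVA or Friedman for VISA-P and NRS:* total change over time, with no comparator.

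**Illustration, before-after test.** Inputs: n = 21 from the design section; the rest assumed, namely two-sided 0.05, no ESWT effect, non-treatment improvement g = 0.3 baseline SD, equal SDs at both times, and test-retest correlation r.

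Standardised change dz = g / √(2(1 − r)); noncentrality = dz × √21; rejection probability from the noncentral t with 20 degrees of freedom (critical value 2.086).

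| r | √(2(1 − r)) | dz | noncentrality | P(significant) |
|---|---|---|---|---|
| 0.4 | 1.095 | 0.274 | 1.255 | 0.22 |
| 0.6 | 0.894 | 0.335 | 1.537 | 0.31 |
| 0.8 | 0.632 | 0.474 | 2.174 | 0.54 |

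The nominal rate is 0.05.

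**Illustration, contrast with healthy tendons.** Two-sample t-test on change, with r = 0.6 and improvement in symptomatic tendons only. Noncentrality = g / (0.894 × √(1/21 + 1/m)) for m healthy tendons, with 19 + m degrees of freedom; m is assumed because the plan does not give it.

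| m | g = 0.3 | g = 0.5 |
|---|---|---|
| 8 | 0.122 | 0.255 |
| 10 | 0.135 | 0.291 |
| 21 | 0.186 | 0.424 |

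The contrast rejects less often than the before-after test because it is noisier. The bias of g remains in its estimate.

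**Regression to the mean, by outcome.** Expected regression is (1 − r) × entry shift, in SD. Patients are selected on pain and impaired function, so this bears most directly on NRS and VISA-P. For SFA or US values, the entry shift is the shift in pain multiplied by the correlation between pain and the parameter. With an assumed 1 SD pain shift and correlation 0.2 to 0.3, the SFA shift is 0.2 to 0.3 SD. The same paired-test formula then gives:

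- shift 0.2, r = 0.9: regression 0.02 SD, dz 0.045, P = 0.05
- shift 0.3, r = 0.6: regression 0.12 SD, dz 0.134, P = 0.09

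On these assumptions, regression to the mean hardly disturbs the micromorphological tests. Spontaneous recovery and altered load are the main threats there.

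**The case against.** The strongest reply is that this is a declared cohort study that monitors change, with no rule in the text attributing that change to ESWT. That stands in part: a reader might infer that the plan will count recovery as effectiveness, but the documents state no such conclusion. What remains is the title and the task given to the healthy group, which together invite the inference.

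A reader might also infer severe regression to the mean throughout. With a 1 SD entry shift, the formula above gives a paired test significant 50% of the time at r = 0.6 and 16% at r = 0.9. The documents do not support using those figures:

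- There is no pain cut-off; limitation in part is enough.
- Baseline follows referral and eligibility, so some regression may already have happened. If correlations are equal across occasions, none remains.
- The paired test is planned for US and SFA parameters, on which patients are not selected.

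A third tempting reading is that sport load and other treatment go unrecorded. History is taken at both examinations with unspecified content, so the fair statement is that these items are not named and no analysis uses them.

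None of these replies supplies a comparator with the disease. Averaging three images does not help either, since it reduces noise within one visit only.

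**Conclusion.** The point holds as a limit on what may be concluded. No planned test separates an ESWT effect from the untreated course of a symptomatic tendon, and the healthy group cannot do the job assigned to it. This follows from the design and needs no numerical assumption.

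The size of the bias cannot be computed from the documents, which give no pain cut-off, SD, test-retest correlation or control-group size. The 22% to 54% rests on an assumed 0.3 SD non-treatment improvement and is an illustration, not an estimate. Regression to the mean matters mainly for NRS and VISA-P; for US and SFA it is indirect and probably small.

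One further ambiguity bears on this. The design section says "Patients in both groups will have same program", which leaves open whether healthy controls also receive ESWT. If they do, they would not show change free of treatment even in normal tendon. The passage needs clarifying.

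**What to change.** 1. **Limit the claim.** State that the study estimates change after ESWT; that healthy and asymptomatic tendons calibrate measurement error and drift in tendons without tendinopathy only; and that no effectiveness claim will rest on a significant before-after change or on its contrast with those tendons.
2. **Name the competing explanations in the data.** List weekly sport days and hours (the units already used for inclusion) and any other tendon treatment among the items collected at existing visits, and report them descriptively beside the change. Do not use a subgroup with unchanged load as a clean check. Load is measured after treatment starts and can itself respond to improvement or worsening, and the subgroup would shrink a sample of about 21.
3. **Optional.** Only if the first ESWT already falls on a different day from the initial examination, repeat VISA-P and NRS before any shocks. Report the difference as short-term variability. The documents give no interval between the two, so it cannot stand for the natural course over 16 weeks.

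The cost is wording, a few minutes of recording per visit and a more modest claim. No new arm or randomisation is needed.

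### Data analysis gives the healthy controls no analysis, and its only between-group test of change in morphology names neither the limb-by-visit interaction nor the pairing of a patient's two limbs

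*Combined protocol and SAP*

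**What the plan says.** Study design and description plans at least 21 patients and, in addition, a "small control group of healthy tendons which will be monitored to observe magnitude of natural changes". It continues: "Patients in both groups will have same program". The size of the control group is not given. The inclusion criteria under Patient selection describe only people with the disease (for example, "has clinical manifestation of PT (pain and impaired function) confirmed by clinician"), with symptoms in one leg only.

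Under Ultrasonographic examination, "three pictures of each leg (symptomatic and asymptomatic) will be saved in long axis", and the three values are averaged. Morphology is measured at baseline and at week 15. Each patient therefore gives four morphology values per parameter: two limbs at two visits.

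Data analysis makes three morphology comparisons:

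- Baseline, between limbs: "Independent t-tests (or Mann Whitney U tests for non-parametric) will be performed for each parameter to compare baseline values between symptomatic and asymptomatic limb".
- Change within limbs, by paired t-test or Wilcoxon test, "evaluated in each group separately (symptomatic, asymptomatic) between baseline and final values".
- Change between groups: "Intergroup statistical significance between baseline and follow-up values of morphological parameters will be evaluated using two-way ANOVA or non-parametric Kruskal-Wallis test".

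For the clinical scales the same section does name a repeated-measures method: "Statistical significance between time periods in VISA-P and NRS parameters will be evaluated using repeated measures ANOVA", or a Friedman test. The healthy controls do not appear in Data analysis.

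**The concern.** Two things are missing and one is wrong as written.

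First, the control group has a stated purpose but no test, estimate or summary that serves it.

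Second, the sentence that should answer whether the treated tendon changed differently does not name the term that answers it (limb by visit). Nor does it say that a patient's two limbs, and the two visits of each limb, are matched. Repeated measures are named for VISA-P and NRS but not for morphology, and two limbs of one person are compared at baseline by an independent-samples test. An unpaired analysis is therefore a realistic reading.

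Third, Kruskal-Wallis is an independent-samples test with no interaction, so it cannot be the non-parametric counterpart of the contrast that is needed.

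The title promises an evaluation of effectiveness on micromorphology. If the layout is settled after the data are seen, the same data can support opposite conclusions. If a reader falls back on the separate within-limb p-values, one significant and one non-significant result does not show that the limbs changed differently.

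**Working it through.** **Inputs.** From the plan: 21 patients, two limbs, two visits. The plan gives no SDs, correlations, expected effects or number of controls. Assumed here: normal data with SD 1 in every cell, pre-post correlation r = 0.5 or 0.7, correlation between a patient's limbs c = 0 to 0.7 (for levels and for changes), two-sided 5% tests. The plan states no figure on this point that could be reproduced.

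**Why pairing matters.** Let D = symptomatic change minus asymptomatic change. The change in one limb has variance 2(1−r), so

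Var(D) = 2(1−r) + 2(1−r) − 2c·2(1−r) = 4(1−r)(1−c).

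- The standard error that keeps the pairing is √[4(1−r)(1−c)/21]. This is √(2/21) = 0.309 at r = 0.5, c = 0, and √(0.36/21) = 0.131 at r = 0.7, c = 0.7.
- An ordinary two-way ANOVA treats the 84 values as independent and uses about √(4/21) = 0.436 in every setting.
- The observed difference needed for significance is therefore about 1.990 × 0.436 = 0.87 SD unpaired (80 df), against 2.086 × 0.309 = 0.64 SD down to 2.086 × 0.131 = 0.27 SD paired (20 df).

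A true difference of 0.5 SD lies well below the unpaired threshold.

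**Simulated rejection rates** (range over the r and c values above):

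| Situation | Unpaired ANOVA interaction | Kruskal-Wallis on change scores | Paired difference in change |
|---|---|---|---|
| No change in either limb | under 1% | 0.1–5% | 4–6% |
| Symptomatic limb changes by 0.5 SD | about 1–12% | 26–53% | about 33–96% |
| Symptomatic limb changes by 0.8 SD | 35–42% | 68–98% | 69–100% |

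**Kruskal-Wallis on raw values in four limb-by-visit cells.** With no change at all and a baseline limb gap of 0.5 SD it rejects in about 28–36% of trials. When the symptomatic limb recovers exactly that gap it rejects less often, in 14–26%. It responds mainly to the limb difference, not to the difference in change.

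**Separate within-limb tests.** If both limbs change equally by 0.4 SD, the symptomatic limb is significant and the asymptomatic limb is not in about 13–24% of trials. The paired difference test stays at about 5%.

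**Control comparison.** Assume 5 to 10 control persons with one tendon each and equal SDs of change. The 95% CI half-width for symptomatic minus control change is t·√(1/21 + 1/m), with Welch degrees of freedom:

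- m = 5: 2.44 × 0.498 = 1.21 SD of change (df 6.1)
- m = 10: 2.10 × 0.384 = 0.81 SD of change (df 17.8)

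**The case against.** The strongest reply is that this is a terse sentence, not a wrong method. Data analysis has just used the word group for the symptomatic and asymptomatic limbs, and a two-way ANOVA of baseline and follow-up values most naturally has limb and visit as factors. Run as a repeated-measures ANOVA, its limb-by-visit term is identical to the paired test of the difference in change. That stands in part: the groups are ambiguous, because both groups in the design section means patients and controls, but they are not undefined. It does not rescue Kruskal-Wallis, which has no interaction and no pairing in any layout, or the baseline test, which is unpaired in so many words.

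The most alarming figures also need a layout that the plan does not state. A reader might infer that the plan is set to produce false positives; the documents do not support that. The 28–36% applies only to Kruskal-Wallis on four raw cells. On change scores it does not reject because of a baseline gap, though it still ignores the pairing. The unpaired ANOVA interaction errs on the conservative side.

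A reader might also take the ANOVA sentence to be the only between-group morphology test. It is not: the baseline limb comparison is another. It is the only one that concerns change.

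Finally, if a patient's two limb changes are uncorrelated, pairing gains nothing over a two-sample test of the changes (34–51% against 36–53% power at 0.5 SD). That stands, but both are far above the unpaired ANOVA interaction in the same setting (8–12%).

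**Conclusion.** The concern holds. The healthy controls have no analysis, the between-group test of change omits the interaction and the pairing, its non-parametric alternative cannot test that interaction, and the baseline limb test is explicitly unpaired. These points rest on the text alone. The sizes rest on the assumed correlations and effects: about 1–12% against about 33–96% power for a 0.5 SD change in one limb.

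It would be tempting to conclude that the paired difference in change measures the effect of shockwave therapy. The documents do not support that. No planned comparison includes an untreated symptomatic tendon, so neither the asymptomatic limb nor a healthy tendon shows spontaneous recovery or regression to the mean in a painful one. The plan also does not say which tendons are treated: the same programme for both groups sits uneasily with controls meant to show natural change. The data for a better contrast are already being collected, so the plan should be corrected before analysis.

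**What to change.** 1. Replace the intergroup sentence with: *For each morphological parameter, the within-patient difference in change (symptomatic-limb change minus asymptomatic-limb change) will be tested by paired t-test or Wilcoxon signed-rank test.* Equivalent parametric forms are the limb-by-visit interaction of a two-way repeated-measures ANOVA, or of a mixed model whose covariance keeps the pairing of limbs within visit. Random intercepts for patient and for limb within patient do not suffice: in four simulated data sets they gave the two-sample t on the changes (2.14, 2.36, 2.61, 2.07) instead of the paired t (2.99, 3.04, 3.88, 4.25).
2. Replace the baseline independent t-test or Mann-Whitney test with a paired t-test or Wilcoxon signed-rank test.
3. Report the healthy tendons descriptively: mean and SD of change, and the difference from symptomatic-tendon change with its 95% CI. If controls are separate persons, use one leg per person, chosen in advance. Averaging both legs would multiply the SD of change by √[(1+c)/2], which is 0.71 at c = 0 and 0.92 at c = 0.7, and so understate the natural variation of a single tendon.
4. Base any between-limb statement on the difference in change, not on separate within-limb p-values. State that, without an untreated symptomatic tendon, it cannot separate shockwave therapy from spontaneous recovery or regression to the mean.
5. Reconcile the shared programme with the aim of observing natural change, and state which tendons receive shockwave therapy, because the meaning of these contrasts depends on it.

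The cost is wording in the analysis plan, with no new patients, visits or measurements. The claim becomes more modest, and the control comparison stays imprecise (half-width about 1.21 to 0.81 SD of change with an assumed 5 to 10 controls).

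### No masking is stated for tendon width or SFA; the SFA images are saved anyway, so coding them and analysing them in random order would protect that step at little cost

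*Combined protocol and SAP*

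**What the plan says.** Initial and final examination gives both examinations of a patient to one examiner: "Both, initial and final examinations in each patient will be performed by only one person (the investigator of the study"). It also fixes the order: "Firstly the anamnestic data will be collected, then the area of greatest pain will be localized by palpation". VISA-P and pain ratings follow, and ultrasound of both legs is last.

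Ultrasonographic examination has width read on the machine: "The values of anteroposterior tendon width at the anteroposterior widest point will be collected using the measuring instruments included in USG machine". No stored frame is mentioned for width. For SFA, "three pictures of each leg (symptomatic and asymptomatic) will be saved in long axis for subsequent micromorphological analysis", and the mean of the three values is analysed. That section does not say who runs the software, when, or with what knowledge of the image's origin.

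Study design and description lists, among the contents of the initial examination, "an ultrasonographic (USG) examination followed by a micromorphological analysis using special software".

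Data analysis uses these readings in tests "to compare baseline values between symptomatic and asymptomatic limb for US and SFA parameters" and in within-limb tests over time: "paired t-tests (or Wilcoxon tests) will be performed for each parameter, evaluated in each group separately (symptomatic, asymptomatic) between baseline and final values". An intergroup comparison of the morphological parameters follows.

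No section mentions masking, blinding, coding of images or order of reading.

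**The concern.** The title outcome is micromorphology, and the study has no randomised comparison. A reader who knows that an image is a final one, or that it shows the painful leg, may lean towards the expected result without intending to.

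- **Knowledge of visit** acts on the baseline-to-final paired tests. Each limb is tested separately, so a visit-related shift in reading enters the test directly.
- **Knowledge of side** acts on the baseline comparison of symptomatic and asymptomatic limbs.
- **The comparison tendons** (the asymptomatic limb and the healthy controls) can reveal a drift common to all tendons. They cannot reveal one confined to the symptomatic tendon, which would also pass into the intergroup test.

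Using one examiner improves consistency but does nothing against expectation. As written, the plan could not show that such a bias is absent.

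**Working it through.** **Step 1: what the examiner knows at the scan.** One person performs both examinations. History, palpation and questionnaires precede ultrasound, so visit, painful side and clinical status are all known by then.

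**Step 2: how each measure is read.**

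| Measure | When read | By whom | Masked? |
|---|---|---|---|
| Width | Live, with the machine's tools | The one investigator | Not stated; on this text it cannot be |
| SFA | From saved images, timing not given | Not named; the design section counts the analysis as part of the examination, which suggests the same investigator | Not stated |

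Caliper placement for width is a direct operator choice. For SFA the plan does not describe what the operator chooses (a region of interest, for example), so the exposure at the reading step cannot be judged from the text.

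**Step 3: what a shift would do to one paired test.** The plan gives 21 as the estimated minimum number of patients, without alpha, power, effect size or SD, so there is no calculation of its own to reproduce. Inputs:

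- n = 21, from Study design and description.
- Two-sided alpha 0.05, assumed.
- No true change, assumed.
- Systematic reading shift b, in SDs of the within-limb change, assumed from 0 to 0.5.

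The test statistic follows a noncentral t distribution with df = 20 and noncentrality b × √21 = b × 4.583. The critical value is 2.086. The false-positive rate is P(T > 2.086) + P(T < −2.086).

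| Shift b (SD of change) | Noncentrality | False-positive rate |
|---|---|---|
| 0 | 0 | 5.0% |
| 0.05 | 0.229 | 5.5% (0.05548) |
| 0.1 | 0.458 | 7.2% |
| 0.2 | 0.917 | 14.1% |
| 0.3 | 1.375 | 25.8% |
| 0.5 | 2.291 | 58.7% |

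This is how any paired t-test behaves at n = 21. It is not an estimate for this trial. No figure is given for the intergroup test, whose model is not specified. None is given for the baseline limb tests either: a true difference is expected there, and bias would distort its size.

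**Step 4: the number of images.** For SFA, 3 images × 2 legs × 2 visits = 12 per patient, and 12 × 21 = 252. One extra width frame per leg per visit would be 1 × 2 × 2 × 21 = 84, for a total of 252 + 84 = 336. Controls are additional, and their number is not stated.

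**The case against.** **The SFA reader is an inference.** A reader might conclude that the unmasked investigator analyses SFA at each examination. The documents do not support that as fact. The one-person rule covers examinations, the list of examination tasks ends with ultrasound, and the images are kept for later analysis with no reader named. Off-line or batch analysis by someone else fits the text too. This objection stands. What remains is that reader, timing and masking are all unstated.

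**The clearest exposure is not in the title outcome.** Caliper placement is plainly open to expectation, but width is not micromorphology. SFA is a software analysis of the speckle pattern, averaged over three images, and may leave the operator little to choose. This also stands, and it limits the expected gain.

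**The illustration says nothing about the actual bias.** A near-zero shift fits the documents as well as a large one. That is correct, and it is why the table starts at zero. The upper rows should not be read as likely.

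**Coding leaves much unprotected.** Probe position, choice of the three images and choice of the widest point are settled at the scan. Re-measuring width off the machine on one frame would not undo those choices and could add error of its own. That is a good reason not to replace the planned width value. It does not argue against coding SFA images that are saved in any case.

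**Two further inferences to avoid.** The plan does not say who applies ESWT, so it cannot be said that the reader also treats. It also says that both groups follow the same programme, which leaves unclear whether control tendons are treated. The contrast between treated and comparison tendons should be drawn with that in mind.

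**Conclusion.** The point holds in limited form. It is certain that no masking is stated, and that width is read live by someone who knows visit and side. It is likely, but not stated, that the same person analyses SFA. Whether SFA is biased as a result depends on operator choices that the plan does not describe.

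The size is unknown. Under the assumptions shown, the effect on one paired test ranges from nothing, through half a percentage point at a shift of 0.05 SD, to a rate of 58.7% at 0.5 SD. The documents do not say where in that range the trial would fall, so the table does not show that the planned results would be unreliable.

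The case for a change rests on the low cost of protecting a title outcome whose images will already be on file. It is an improvement worth making rather than a flaw that invalidates the study.

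**What to change.** State who reads width and who analyses SFA, when, and with what knowledge of visit and side. Then add to Ultrasonographic examination:

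> After the last final examination, all saved SFA images (12 per patient, 252 for 21 patients, plus those of the controls) will be stripped of patient, side, date and group labels and given random codes by a script. They will be analysed in random order, with the key kept closed until all SFA values are locked.

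**Optional:** save one caliper-free frame per leg per visit (84 for 21 patients) and re-measure width on the coded frames as a sensitivity analysis. The planned on-machine width stays the analysed value. This needs a way to measure against the image's depth scale, which the plan does not mention.

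**Limitations to list:** live width, probe placement, image choice, NRS and VISA-P remain unmasked, and visible pathology may reveal the side, so visit is better hidden than side.

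**Cost:** a small scripted coding task, safe keeping of the key, and SFA analysis held until the end. Image quality must still be checked on the day. No extra visit or second reader is needed. No section uses an SFA value for eligibility or treatment. The treatment site is set by the live scan ("applied semi-statically to the most US defined pathological area in patellar tendon"), which is unchanged. The gain may be small if the software leaves the operator few choices.
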